--	--

	
stored as a back-up. For participants who entered in the blinded version and then were unblinded and vaccinated, baseline serology will not be performed again, taking the values from the baseline visit performed at the first visit.
 

• For linking purposes, each participant will be assigned a treatment identification number. The number of each administered treatments must be recorded in the eCRF.

• Injection of study vaccine After completing all prerequisite procedures prior to injection, one dose of the assigned vaccine will be administered IM in the deltoid muscle, preferable of the non-dominant arm. If the investigator or delegate determines that the participant's health on the day of administration temporarily precludes administration, the visit will be rescheduled within 1 week. There will be a 15-minute wait after each vaccination to monitor for any rare anaphylactic reaction. At Day 56 after first vaccination, all participants will get a second injection of the investigational vaccine (Second Injection Visit)

• Safety participant contacts Every 4 Weeks for 52 weeks there will be telephone calls following vaccination. They will be used to continuously collect any SAE and MAE data. Participants can report any AE they experience at any time during the study period; however, only SAE and MAE will be entered into the eCRF. In-person visits will occur for Day 28 visit (to collect solicited and unsolicited events, Day 56 (Second Injection Visit), Day 84 and Week 24, and Week 52 visits.

• Efficacy participant contacts All participants will have efficacy participant contacts weekly, for 52 weeks following vaccination. There will be approximately 52 efficacy participant contacts. All efficacy participant contacts will be emails, although other methods such as phone calls or text messages, if preferred, are acceptable. Each participant contact needs to be recorded in the study electronic case report form. The purpose of these participant contacts is to ask if the participants had any symptoms of illness they may be experiencing, regardless of severity. Any possible COVID-19 relevant symptoms will trigger laboratory testing for SARS-CoV-2 infection.

• Illness participant contact visits (Confirmed or suspected infection during study) Participants will be provided detailed instructions regarding the signs and symptoms of COVID-19 disease at each participant contact and will be instructed to seek medical attention and notify study staff should symptoms occur. Symptoms of interest include fever, cough, difficulty breathing, diarrhea, nausea, vomiting, prolonged fatigue, respiratory symptoms, chills, myalgia, sore throat, headache, congested/runny nose, pneumonia, difficulty swallowing, anosmia/ageusia (loss of sense of smell/taste), and neurological events. During the observation period of the study, if any of these symptoms develop in a participant, he/she should immediately follow local procedures for care of suspected COVID-19 illness and contact the study team. If a COVID-19 infection is found during the study, a case investigation will be undertaken according to locally recommended procedures.

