	
A new e-diary or paper diary card to record solicited and unsolicited AE from Second Injection will be provided at Second Injection Visit- Day 56. The data in the completed e-diary or diary card provided during the Day-56 visit will be reviewed and data will be collected at visit on Day 84. Further details are outlined in Section 3.7 and 5.1.
 
All participants will be contacted on a weekly basis to be reminded to report any signs or symptoms of illness to study staff. Participants will either be contacted by the site weekly, or they will receive an automated message (email) with a link to answer questions about whether or not they had an SAE, an MAE or COVID-19 symptoms. Participants will also be asked on their day 7 contact about any events that might meet a pause or early termination criterion. The reporting and monitoring of any participant illness are consistent with meeting the primary efficacy objective. If a participant becomes ill, they will be asked to immediately proceed to the site designated by their local study team where they will be assessed and treated as deemed appropriate. Participants will also receive a telephone call every 4 weeks, to evaluate for the incidence of any SAE or MAE.
 
A subset of 50 participants will have additional immunologic testing performed, following the same visit schedule, to evaluate T-cell response to the Ad5-nCoV vaccine.
 
If a participant demonstrates signs or symptoms of illness, an unplanned in-person visit may occur for evaluation and possible treatment. If, for any reason following an electronic participant contact, the investigator would like to conduct an in-person visit (at home or at the site) with a participant, they may do so at their discretion.

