Pause and early termination	
Study Suspension Criteria
 
If a suspension criterion is met, the study will be put on hold, and further injections will not occur until a safety review has been conducted. Should a suspension criterion be met, the local PI will inform the PIs, Sponsors, and NRA within 24 hours.
 
Suspension criteria includes:
 
Grade 3 or greater AE occurring in >15% of participants will constitute study suspension criteria. To be included as suspension criteria, AE must begin within three days after study injection (day of injection and 2 subsequent days) and persist at Grade <math>\geq 3</math> on three consecutive days, depending upon symptom severity and kinetics.
 
A suspected, unexpected serious adverse reaction (SUSAR) that is life-threatening or results in death will warrant study suspension.
 
Other study suspension criteria include if the IDMC assessed the potential safety risks to be harmful, or if the vaccine candidate might be ineffective.
 
Study Early Termination Criteria
 

• Required by the sponsor, or

- Required by the regulatory authority, or
- Required by an institutional review board (IRB)

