#### 3.2 Study Groups

A total of 500 participants will be enrolled to receive the vaccine. All participants will be monitored for solicited adverse events for 7 days, unsolicited adverse events for 28 days, SAEs and MAEs for the one year duration of the study, and antibody measurements at baseline, Day 28, Day 84, week 24, and week 52. A subset of 50 participants will have cellular immunity measured at those same intervals.

This protocol amendment provides for unblinding of participants who were entered into the study in the double-blind schedule. For participants who entered the double-blind schedule, the visit process will be as follows:

a) Sites will receive an unblinding list detailing participants who received placebo or study vaccine. Participants who received placebo will be invited to continue in the study under the

open-label study scheme and should make visits from V1.B (first vaccine) onwards, after signing the informed consent, completing visits on day 28 (V2.B), day 56 (second dose) (V3.B), day 84 (V4.B), week 24 (V5.B) and week 52 (V6.B). In this group of participants already enrolled, no antibody dosage collection will be performed at the V1B visit; the V1 values at study entry will be taken. The letter B is added to the visits to differentiate this group of participants who must reorganize the schedule of visits from the administration of the first dose of CoVID vaccine after the unblinding. The procedures for this group are detailed in Table 2.

b) Participants who, after the unblinding, are found to have received study vaccine at the initial visit, will complete the visits established by protocol together with the administration of dose 2 of the study (day 56) onwards, after signing the informed consent. In this group of participants there will be no changes in the nomenclature of the visits.

For both arms (placebo and study vaccine), efficacy contacts are restarted with the second injection visit.

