**Detailed description of study procedures and interventions is outlined in Section 5.1**

**Table 2. Procedures for the group of participants assigned to placebo arm. In-person visit**

	Visit 1.B	Visit 2.B	Visit 3.B	Visit 4.B	Visit 5.B	Visit 6.B
Intervention	Day 0 (First Injection)	Day 28	Day 56 (Seco nd Inject ion)	Day 84	Week 24	Week 52
Visit window		+/- 7 days	+/- 7 days	+/- 7 days	+/-14 days	+/-14 days
Informed Consent						
Review Consent		•	•	•	•	•
Collect Demographic and Participant Contact Information						
Blood sample collected for HIV viral load and CD4/CD8 counts					•	•
Urine Pregnancy test- women of childbearing potential	•		•			
Review Inclusion and Exclusion criteria [2]			•			
Medical History	•		•			
Check and record prior concomitant medication and vaccines	•		•			
Check and record intercurrent medical conditions	•		•			
Check Contraindications to vaccine	•		•			

Pre-injection vital signs	●		●					
Study group and treatment number allocation								
Screening conclusion								
Administration of Study Product	●		●					
Safety participant contact (Phone call or in-person visit)				Every 4 weeks (Day 28, 56 and 84 is in person)				
Efficacy participant contact (message) (a)				Weekly from Day 7- week 52 (visit window: +3 days)				
Safety participant contact: in-person visit	●	●	●	●	●	●	●	
Paper diary card or e-diary provided to participant	●		●					
E-diary or diary card reviewed with participant and data collected and uploaded to eCRF		●		●				
Immunogenicity participant contact: in-person visit		●	●		●		●	
Blood Sample Collected for ELISA and neutralizing Antibody testing (~25mL)		●		●	●		●	
Blood Sample Collection for ICS testing (~30mL) (b)		●		●	●		●	
Study conclusion							●	

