## Subject management algorithm

[figure not shown]

Figure 1. Procedure algorithm for efficacy contacts

After COVID-19 diagnosis, participants will be referred locally for management, as required. Data to determine whether these participants meet criteria for severe COVID-19 or if they receive antivirals that could modify the likelihood of severe COVID-19 will be collected. Study participant contact for COVID-19 disease is planned to last for at least 12 months.

Participants will have contacts via email, text, or phone message on Days 7, 14, 21, 35, 42, 49,, 63, 70, 77, 91, 98, 105, 112, 119, 126, 133, 140, 147, 154, 161,175, 182, 189, 196, 203, 210, 217, 224, 231, 238, 245, 252, 259, 266, 273, 280, 287, 294, 301, 308, 315, 322, 329, 336, 343, 350, and 357. Participant contacts on Days 56, 84, 112, 140, 196, 224, 252, 280, 308, and 336 will have a phone call, in addition to an email or text message. Day 28, 56, 84, 168 (week 24), and 364 (week 52) will be an in-person visit to accommodate the diary reviews and immunological testing.

*The visit window for Efficacy participant contact is +3 days.*

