### 11.1 Study Suspension Criteria

If a suspension criterion is activated, the study will be put on hold, and further injections will not be administered until a safety review has been conducted. Should a suspension criterion be activated, the local PI will inform the global PI, Sponsors, and NRA within 24 hours.

Suspension criteria include:

- More than 15% of participants experience a Grade 3 AE beginning within 3 days after study injection (day of injection and 2 subsequent days) and persisting at Grade  $\geq 3$  on three consecutive days depending upon symptom severity and kinetics.
- A suspected, unexpected serious adverse reaction (SUSAR) occurs that is life-threatening or results in death.
- The IDMC assessed the potential safety risks in clinical studies.
- The IDMC assessed that the vaccine candidate might be ineffective.

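### The pause-event question behind the >15% Grade ≥3 suspension rule is stated only for a day 7 contact, so non-serious, unattended Grade 3 reactions after dose 2 are left to the Day 84 diary review

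*Protocol*

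**What the plan says.** **The rule.** The synopsis (Pause and early termination) sets a threshold of more than 15% of participants with a Grade 3 or greater event. To count, an "AE must begin within three days after study injection (day of injection and 2 subsequent days) and persist at Grade" 3 or above on three consecutive days. Section 11.1 repeats it: "More than 15% of participants experience a Grade 3 AE beginning within 3 days after study injection". Neither version limits the injection to the first, and every participant is due active vaccine on Day 0 and Day 56. If the rule is met, further injections stop until a safety review.

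**The question that feeds it.** The synopsis visit plan states: "Participants will also be asked on their day 7 contact about any events that might meet a pause or early termination criterion". Section 3.3, the parallel text in the body, describes the same weekly contacts but does not include this sentence.

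**Contact schedule.** Section 3.5 lists "contacts via email, text, or phone message on Days 7, 14, 21, 35, 42, 49,, 63, 70, 77" and onward, so the contact one week after the planned second dose is called Day 63. For participants who entered under the blinded design, section 3.2 says: "For both arms (placebo and study vaccine), efficacy contacts are restarted with the second injection visit". Table 2, for the former placebo group, has them "Weekly from Day 7- week 52 (visit window: +3 days").

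**Dose 2 diary.** The data in the diary "provided during the Day-56 visit will be reviewed and data will be collected at visit on Day 84" (synopsis, Visit plan; sections 3.3 and 5.1 agree).

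**The concern.** A stopping rule works only if its data arrive while stopping can still protect someone. This rule needs two items for each event: the grade, and whether that grade held on three consecutive days. Both exist within days of the injection. The plan has a day 7 check aimed at such events, but as written it most naturally attaches to dose 1. For dose 2, the stated point at which diary intensity data reach study staff is the Day 84 visit. Participants who have had dose 2 receive nothing further, but others may still be receiving first or second doses in the meantime. They are the people the rule is meant to protect.

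**Working it through.** The protocol gives no figure of its own to reproduce here. The check is calendar arithmetic, followed by a comparison of the reporting routes.

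**Inputs.** Dose 2 on Day 56 ±7 and Visit 4 on Day 84 ±7 (Table 1). Weekly contacts with a +3 day window, including Day 63 (section 3.5). Onset on the day of injection or the next 2 days, with three consecutive days at Grade ≥3 (synopsis; section 11.1). 500 participants (section 3.2).

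**When a qualifying event is complete.** Onset on day 0, 1 or 2, plus two more days, gives day 2, 3 or 4 after injection.

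**Nominal timing after dose 2.**
- Diary review: 84 − 56 = 28 days.
- Existing Day 63 contact: 63 − 56 = 7 days.
- Difference: 28 − 7 = 21 days.
- From a completed event to diary review: 28 − 4 = 24 to 28 − 2 = 26 days.

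**With visit windows** (assumed independent and counted from Day 0). Dose 2 falls on Days 49 to 63, and Visit 4 on Days 77 to 91.
- Diary review: 77 − 63 = 14 to 91 − 49 = 42 days after dose 2.
- Contact tied to the actual injection date: 7 to 7 + 3 = 10 days.
- Time gained by the anchored contact: 14 − 10 = 4 to 42 − 7 = 35 days.
- Contact fixed at Day 63 (+3): 63 − 63 = 0 to 66 − 49 = 17 days after dose 2. A fixed contact can come before the event is complete, so the question has to follow the injection date.

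**Size of the trigger.** 0.15 × 500 = 75, so more than 15% means at least 76 participants. This assumes a denominator of all 500, which the protocol does not define.

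**Injections given in the interval.** No enrolment rate is stated, so the number cannot be derived. At an assumed r injections per week, 21 days is 3r: 15, 30 or 60 for r = 5, 10 or 20. These rates are illustrations only.

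**Other routes after dose 2.**

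| Route | What it can show before Day 84 | Grade and three-day persistence stated? |
|---|---|---|
| Weekly contact (synopsis; sections 3.3, 5.1) | SAE, MAE, COVID-19 symptoms, other illness symptoms | No |
| Four-weekly call | SAE and MAE; the next after Day 56 is due on Day 84 | No |
| Instruction to call at once (section 7) | Anything the participant perceives as serious | No |
| SAE and SUSAR reporting; IDMC review of Grade 4 events (sections 7.2, 11, 11.1) | Serious or Grade 4 events | Not needed for these |
| Diary | All solicited events | Holds daily intensity; stated review is Day 84 |

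There are 10 solicited events (3 local, 7 general). Six are on the suspect-case symptom list in section 3.5: fever, headache, nausea, vomiting, diarrhea and muscle aches. The other 10 − 6 = 4 (injection-site pain, redness, swelling, and drowsiness) are not named there.

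**The case against.** The case against is substantial, and part of it stands.

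- **The day 7 contact may be meant per dose.** The sentence comes straight after the text on the second diary, and the protocol elsewhere uses day labels relative to a dose without repeating them for dose 2 (Table 3, for example). For formerly blinded participants, restarting contacts at the second injection could itself put day 7 after dose 2. These readings are possible, but none is stated, and section 3.5 numbers contacts from dose 1.
- **Many events would surface earlier.** The synopsis says the weekly contacts are "to ask if the participants had any symptoms of illness they may be experiencing, regardless of severity", so the symptom list does not cap what can be reported. Section 7 tells participants to call immediately about anything they perceive as serious, and a Grade 3 reaction lasting three days may well prompt that call. This narrows the gap. It does not close it, because none of these routes is stated to record grade and persistence.
- **An e-diary could be read between visits.** The protocol neither provides for this nor excludes it, and paper diaries are allowed.
- **The dose 1 question is no more specific.** This is correct: it is not stated to collect grade or persistence either. The fix should therefore cover both doses.
- **The trigger is high and may never be reached.** The protocol reports Grade 3 reactions in 9% at the higher phase II dose and significantly fewer at the dose used here. Those were healthy adults, and the Ad5-nCoV summaries in section 1.2 give no second-dose results.

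A reader might infer that Grade 3 reactions after dose 2 stay invisible until Day 84, or that the rule cannot operate after dose 2. The documents do not support either. Earlier routes exist for most severe events, and spontaneous reports are invited.

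**Conclusion.** The point holds in a limited form. The suspension rule covers both doses, but the one question stated to feed it is not clearly asked after dose 2. For a non-serious Grade 3 reaction without medical attendance, the stated collection point for grade and duration is nominally 28 days after dose 2 (14 to 42 with windows). A contact tied to the injection would give them at 7 to 10 days.

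This rests on three readings: that an unrestricted reference to study injection includes dose 2, that day 7 follows the contact numbering in section 3.5, and that visit windows count from Day 0. The number of people injected during the delay is not computable from the document, and no harm has been shown. The change is still worth making: it makes a safety rule workable for both doses, and what participants are asked and when belongs in the protocol rather than the analysis plan.

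**What to change.** In the synopsis visit plan and sections 3.3 and 3.5, state that the pause-event question is asked at the weekly contact 7 days (+3) after the actual date of each injection. This should cover dose 1 and dose 2, including Visits 1.B and 3.B. For both doses, specify that it asks whether any Grade 3 or higher event began on the injection day or the following 2 days, and whether it stayed at Grade 3 or higher on three consecutive days. Anchoring to the injection date also settles the uncertainty between section 3.2 and Table 2 for this question.

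The cost is one question in a contact that already takes place, asked once per dose. No visit or sample is added.

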**Process of Suspension of Injection and/or Study Modification**

In the event that a safety signal is observed, the IDMC might recommend that the sponsor suspend injections of all group participants (early termination of study) or selected groups.

In this case, for impacted groups:

Participants who are already injected will continue all visits as planned.

Participants who signed an informed consent but have not received any study product will be informed that their study participation will be stopped.

**Statistical analysis****Statistical Analysis Plan (SAP)****Analysis of Demographic and Baseline Characteristics**

Demographic and baseline characteristics will be summarized overall and then by treatment group using appropriate descriptive statistics. Continuous data will be summarized using the number of observations, mean, standard deviation, median, minimum and maximum. Categorical data will be summarized using frequency counts and percentages. 95% confidence intervals will be reported, but no statistical hypothesis testing will be conducted. Results will be presented for all participants.

**Analysis of Efficacy**

Due to limited sample size, no formal efficacy hypothesis will be tested as primary objective. A listing of baseline characteristics, treatment group and outcome for virologically confirmed (PCR positive) COVID-19 cases will be produced. An exploratory efficacy analysis of Ad5-nCoV in preventing asymptomatic disease of COVID-19 will be conducted at the end of the study.

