--	---

- If COVID-19 is suspected, the participant will have a nasopharyngeal/throat swab taken. Testing for COVID-19 by PCR will be performed at the local clinical laboratory.
- If negative, the test will be repeated in 3 days from the first testing day.
- All attempts will be made to re-test positive samples in a reference laboratory. If the local lab is also a reference laboratory, then a confirmatory sample is not required.
- If the PCR is positive, nasopharyngeal/throat swabs will be taken every 2 days times 3 and then weekly and tested for COVID-19 by PCR until a negative sample is obtained.
- A serum sample (10mL blood) will be collected at the time of illness presentation and testing for SARS-CoV-2 anti-N IgG antibodies will be performed at Nexelis Laboratories (Canada).
- At Day 21-28 post-illness, a second serum sample will be taken and sent to the central laboratory for anti-N IgG.
- Participants who were PCR negative will also have that visit on day 21-28, where they will be tested for SARS-CoV-2 antibodies (Nexelis Laboratories (Canada)). This visit takes place at the research site where the participant is enrolled.
- Participants who develop COVID-19 infection post-vaccination will be carefully monitored for vaccine-related disease enhancement in collaboration with their primary physician who will be encouraged to obtain specimens in accordance with the Brighton Collaboration definition (Munoz, 2020), including a serum sample tested locally for C-reactive protein (CRP), ferritin, and procalcitonin, biomarkers that have been associated with predicting more severe disease outcome in infected patients.

Participants who develop COVID-19 disease will continue to be followed for other study outcomes by telephone while in isolation, and at the study site once recovered and released from isolation by public health officials.

- **Final serology**

Approximately 25mL of whole blood will be collected and will then be separated into serum at week 52. The serum will be aliquoted. The first aliquot will measure anti-N IgG antibodies, at the Nexelis Laboratories (Canada). The second aliquot will be stored as a back-up. The one-year antibody levels measured against anti-N IgG antibodies will be compared to the participant's baseline levels to evaluate the exploratory efficacy analysis against asymptomatic infection.

- **E-diary and Diary Cards**

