### **Exploratory Objective Endpoints**

- Efficacy of two doses of Ad5-nCoV in preventing symptomatic disease of COVID-19 (confirmed by PCR) occurring 14 and 28 days to 52 weeks after vaccination, regardless of severity.
- Efficacy of two doses of Ad5-nCoV in preventing virologically (PCR) or serologically (four-fold increase in SARS-CoV-2 anti-N IgG from pre-immunization to post symptom, defined as Day 21-28 post illness blood test, or pre-symptom to post-symptom blood test) confirmed COVID-19 disease occurring 14 and 28 days to 52 weeks after vaccination, regardless of severity.
- Efficacy of Ad5-nCoV in preventing severe COVID-19 disease caused by SARS-CoV-2 infection from 14 and 28 days to 24 and 52 weeks after vaccination.
- Efficacy of Ad5-nCoV in preventing asymptomatic disease of COVID-19 (confirmed by N IgG antibody on week 52 after vaccination).
- Severity of COVID-19 cases among vaccine recipients (based on WHO or FDA criteria) as compared to the control group, to measure antibody-mediated disease enhancement (ADE).

- SARS-CoV-2 virus shedding in COVID-19 cases that occurred 28 days to 52 weeks after vaccination (detection of viral nucleic acid every 2 days after being confirmed).
- Genotype of SARS-CoV-2 virus isolates of COVID-19 cases that occurred 28 days to 52 weeks after vaccination.
- Suspected but unconfirmed cases of COVID-19 (either because of negative or no tests)
- Evaluate incidence of suspected but unconfirmed cases of COVID-19 (either because of negative or no tests).

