#### **Analysis of exploratory endpoints**

Analysis of exploratory endpoints will be descriptive. PCR confirmed positive subjects will be classified as having severe or non-severe disease. Severity of disease, SARS-CoV-2 virus shedding and Genotypes SARS-CoV-2 virus isolates will be listed by subject and date, along with demographic data, including the study centre. Suspected but unconfirmed cases and asymptomatic cases will also be listed.

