  - Participants will donate approximately 25mL of whole blood on First Injection Visit, Day 28, Day 84 and Week 24, and Week 52, as described above. Whole blood will be separated into serum, and then aliquoted. These in-person visits will occur at participants' local study site. A baseline antibody titer against SARS-CoV-2 will be established from the blood sample collected on First Injection Visit, as outlined in the "baseline serology" description. In addition, these samples will also be used to evaluate for additional immunogenicity objectives. Serum collected will be analyzed for the seroconversion rate of S-RBD IgG antibody, GMT of S-RBD IgG antibody, GMI of S-RBD IgG antibody, seroconversion rate of pseudo-virus neutralizing antibody, GMT of pseudo-virus neutralizing antibody, and the GMI of pseudo-virus neutralizing antibody at Day 28, Day 84, Week 24, and Week 52. The second aliquot will be shipped by the central laboratory to Nexelis Laboratories, where it will be stored as a back-up.
  - **Blood collection for ELISpot and ICS measurement**
    - In a subset of approximately 50 participants, approximately 30mL of whole blood will be collected from participants on First Injection Visit, Day 28, Day 84 and Week 24, and Week 52, as described above. TNF, IL-4, IL-5, IL-13 will be measured by ICS on Day 28, Day 84 and Weeks 24 and 52 after vaccination. PBMC will be shipped on dry ice to Nexelis Laboratories (Canada).

- **Final serology**

Participants will have an in-person visit on Month 12. Approximately 25 mL of whole blood will be collected from each participant and separated for serum into two aliquots. The first aliquot will measure antibodies against SARS-CoV-2, at Nexelis laboratories. The second aliquot will be shipped by Nexelis laboratories to the Sponsor, where it will be stored as a back-up. The one-year antibody levels measured against SARS-CoV-2 will be compared to

the participant's baseline levels to evaluate the exploratory efficacy analysis against asymptomatic infection.

*The visit window for immunogenicity in-person visits of Day 28 and Day 84 is +/- 7 days.  
The visit window for immunogenicity in-person visits of Week 24, and Week 52 is +/- 14 days*

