## 9. OUTCOME MEASURES AND STATISTICAL METHODS

### 9.1 Sample Size Estimation

Since this is an open, non-comparative study that seeks to observe the impact of vaccination on the evolution of HIV disease, a sample size defined by statistical criteria is not established.

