### 9.3.5 Analysis of exploratory endpoints

#### Exploratory endpoints

- Efficacy of two doses of Ad5-nCoV in preventing symptomatic disease of COVID-19 (confirmed by PCR) occurring 14 and 28 days to 52 weeks after vaccination, regardless of severity.
- Efficacy of two doses of Ad5-nCoV in preventing virologically (PCR) or serologically (four-fold increase in SARS-CoV-2 anti-N IgG from pre-immunization to post symptom, defined as Day 21-28 post illness blood test, or pre-symptom to post-symptom blood test) confirmed COVID-19 disease occurring 14 and 28 days to 52 weeks after vaccination, regardless of severity.
- Efficacy of two doses of Ad5-nCoV in preventing severe COVID-19 disease caused by SARS-CoV-2 infection from 14 and 28 days to 24 and 52 weeks after vaccination.
- Efficacy of two doses of Ad5-nCoV in preventing asymptomatic disease of COVID-19 (confirmed by N IgG antibody on week 52 after vaccination).
- Severity of COVID-19 cases among vaccine recipients (based on WHO or FDA criteria) as compared to the control group, to measure antibody-mediated disease enhancement (ADE).
- SARS-CoV-2 virus shedding in COVID-19 cases that occurred 28 days to 52 weeks after vaccination (detection of viral nucleic acid every 2 days after being confirmed).
- Genotype of SARS-CoV-2 virus isolates of COVID-19 cases that occurred 28 days to 52 weeks after vaccination.
- Suspected but unconfirmed cases of COVID-19 (either because of negative or no tests).
- Evaluate incidence of suspected but unconfirmed cases of COVID-19 (either because of negative or no tests).

Analysis of endpoints will be descriptive. PCR confirmed positive subjects will be classified as having severe or non-severe disease. Severity of disease, SARS-CoV-2 virus shedding and Genotypes SARS-CoV-2 virus isolates will be listed by subject and date, along with demographic data, including the study centre. Suspected but unconfirmed cases and asymptomatic cases will also be listed.

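### The asymptomatic-infection analysis is called efficacy, but the amended study has no comparator, so it can give a proportion infected and not an efficacy estimate

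*Protocol*

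**What the plan says.** The synopsis, under Analysis of Efficacy, says "An exploratory efficacy analysis of Ad5-nCoV in preventing asymptomatic disease of COVID-19 will be conducted at the end of the study". Section 9.3.2 makes the same commitment. Both sections explain the absence of a formal efficacy hypothesis by the limited sample size.

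The contrast is described under Final serology. For asymptomatic infection the synopsis has "The one-year antibody levels measured against anti-N IgG antibodies will be compared to the participant's baseline levels to evaluate the exploratory efficacy analysis against asymptomatic". Section 5.1 has "The one-year antibody levels measured against SARS-CoV-2 will be compared to" the participant's own baseline, and names no antigen. Section 12.2 supplies the case rule: no illness visit, and seroconversion to N from injection to Week 52.

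The endpoint is listed in the synopsis as "Efficacy of Ad5-nCoV in preventing asymptomatic disease of COVID-19 (confirmed by N IgG antibody on week 52 after vaccination") and in Section 9.3.5 as "Efficacy of two doses of Ad5-nCoV in preventing asymptomatic disease of COVID-19 (confirmed by N IgG antibody on week 52 after vaccination"). The neighbouring endpoints on PCR-confirmed, serologically confirmed and severe disease are worded as efficacy too, as are the matching objectives in the synopsis and Section 2.2.4.

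On design, Section 9.1 begins "Since this is an open, non-comparative study that seeks to observe the impact of vaccination on the evolution of HIV disease". Sections 3.1 and 3.2 have all 500 participants receiving vaccine. Section 3.2 invites former placebo recipients to be vaccinated and reuses their original V1 antibody values, with no new sample at V1.B. On output, the synopsis and Section 9.3.5 call the exploratory analyses descriptive and add: "Suspected but unconfirmed cases and asymptomatic cases will also be listed".

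**The concern.** Vaccine efficacy is a contrast between vaccinated and unvaccinated people at the same risk. The plan promises an efficacy analysis, but the only comparison it describes is before versus after within vaccinated people. The result depends on how much virus circulated that year. A low proportion in a quiet season could be read as protection, and a high one during a wave as vaccine failure.

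The explanation by sample size adds to the confusion, because it suggests that a larger cohort of the same design could answer the question. It could not.

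At stake is how the report describes infection in vaccinated people living with HIV: as a frequency that the data support, or as an efficacy finding that they do not.

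**Working it through.** **No figure to reproduce.** The protocol gives no event count, power or efficacy value for this analysis. The check is whether efficacy can be estimated from the planned data at all.

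**Inputs from the protocol**
- Enrolled and vaccinated: 500 (Section 3.2).
- Contrast: Week 52 antibody against own baseline (synopsis and Section 5.1, Final serology).
- Case: N seroconversion with no illness visit (Section 12.2).
- Second dose at Day 56; Week 52 is Day 364 (Sections 3.1 and 3.5).
- Attack rate in unvaccinated people: not given and not collected.

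**Step 1: formula.** VE = 1 - ARv / ARu, where ARv and ARu are the attack rates in vaccinated and unvaccinated people. The plan supplies ARv only.

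**Step 2: what the data can give.** Assumed case counts out of 500, with Clopper-Pearson 95% intervals:

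| Cases | Proportion | Exact 95% CI |
|---|---|---|
| 25 | 5.0% | 3.3% to 7.3% |
| 50 | 10.0% | 7.5% to 13.0% |
| 100 | 20.0% | 16.6% to 23.8% |

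The real denominator will be below 500 to the extent that participants are anti-N positive at baseline or lack a Week 52 sample.

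**Step 3: what the same data would imply for efficacy.** Fix ARv at 10.0% (50/500) and vary the assumed ARu:

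| Assumed ARu | VE = 1 - 0.10/ARu |
|---|---|
| 5% | -100% |
| 10% | 0% |
| 15% | 33% |
| 20% | 50% |
| 30% | 67% |
| 40% | 75% |

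Both the sign and the size come from a rate that the study does not observe. A larger sample narrows the interval in step 2 and leaves step 3 unchanged, so sample size is not the limit.

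**Step 4: can the superseded placebo phase supply ARu?** The endpoint is N IgG at Week 52 after vaccination. Former placebo recipients have no antibody sample at V1.B, so no serum closes their placebo period. An infection acquired on placebo would appear as a change from V1 to the Week 52 visit after vaccination. The number of such participants is not stated.

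**Step 5: what the window covers.** Baseline is taken before dose 1. Of the 364 days, 56 (56/364 = 15%) come before dose 2, and 84 (84/364 = 23%) come before 28 days after dose 2. For former placebo recipients the window also includes the unvaccinated time from V1 to V1.B.

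**Step 6: which antibody.** The synopsis compares anti-N; Section 5.1 says only antibodies against SARS-CoV-2. The vaccine expresses S, so an S-based reading of Section 5.1 would pick up the vaccine response itself.

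**The case against.** The strongest reply is that little depends on the label. No formal efficacy hypothesis is tested, no efficacy estimator or success rule is given, the exploratory analyses are called descriptive, and the named outputs are listings. No primary conclusion rests on this analysis. That stands, and it limits the weight of the point. It does not remove it, because a descriptive result presented as efficacy is still mislabelled.

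Three stronger readings are tempting, and the documents do not support them.

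- A reader might infer that the report is bound to contain a numerical efficacy result. Nothing in the protocol specifies one.
- A reader might infer that infection frequency will not be estimated and that cases will be listed without a denominator. Descriptive analysis does not exclude proportions, saying that cases will be listed does not say that only a listing is produced, and Section 9.3 leaves method details to the SAP, which is not at hand.
- A reader might take the result as an attack rate in a fully vaccinated cohort. The window opens before dose 1 and, for former placebo recipients, includes placebo time.

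The sample-size explanation may be left over from the placebo-controlled design that Section 1.3 describes; that is an inference. The decision it supports, not to test efficacy, is right. Only the reason needs correcting.

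**Conclusion.** The point holds as a mismatch between the stated aim and the design. With all participants vaccinated and only a within-person contrast, the study can estimate the proportion with asymptomatic N seroconversion. It cannot estimate efficacy against asymptomatic infection, and the symptomatic and severe endpoints worded as efficacy have the same limit. The true reason is the missing comparator.

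This conclusion follows from the design and needs no numerical assumption. The figures only illustrate it: an assumed 50/500 fits any efficacy from -100% to 75% as the assumed unvaccinated attack rate moves from 5% to 40%. They do not measure harm. The correction should be made, but the impact is limited because the analysis is exploratory and descriptive.

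**What to change.** 1. **Synopsis, Analysis of Efficacy, and Section 9.3.2.** Replace the efficacy analysis with the proportion of participants anti-N negative at baseline who meet the Section 12.2 asymptomatic case definition (N seroconversion by Week 52 and no illness visit), with an exact binomial 95% CI. Do not give a person-time rate for this endpoint, because the infection dates are unknown.
2. **Former placebo recipients.** Report them separately, since their baseline is the original V1 sample and their window includes unvaccinated time.
3. **Section 5.1, Final serology.** Name anti-N, as the synopsis does.
4. **Symptomatic and severe COVID-19 objectives and endpoints** (synopsis, Sections 2.2.4 and 9.3.5). Reword them as incidence per 100 person-years from the stated post-vaccination start, with exact Poisson 95% CIs, alongside the listings. As an illustration, an assumed 50 cases in an assumed 480 person-years gives 50/480 = 10.4 per 100 person-years (exact 95% CI 7.7 to 13.7).
5. **Reason.** State that no efficacy conclusion will be drawn because there is no comparator, and drop the sample-size explanation.

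The cost is protocol and SAP wording, plus a person-time calculation for symptomatic cases from contacts and illness visits already planned. The downside is that the report can no longer claim an efficacy result.
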